5.6.4 Vital Signs

Descriptive statistics for vital signs parameters (e.g., systolic and diastolic BP, pulse, respiratory rate, temperature, weight) and changes from baseline will be presented by visit and treatment group.

Descriptive statistics for vital signs parameters (e.g., systolic and diastolic BP, pulse, respiratory rate, temperature, weight) and changes from baseline will be presented by visit and treatment group.

In addition, clinically notable vital sign values will be identified using the criteria in [Table 2](#). The clinically notable vital sign values will be summarized using frequency count at each visit by treatment group.

Table 2 Vital Sign Criteria

Variable	Criterion value ^a	Change relative to baseline ^a	Clinically notable range
Pulse rate	>120 bpm	Increase of 15 bpm	H
	<50 bpm	Decrease of ≥ 15 bpm	L
Systolic BP	>180 mmHg	Increase of ≥ 20 mmHg	H
	<90 mmHg	Decrease of ≥ 20 mmHg	L
Diastolic BP	>105 mmHg	Increase of ≥ 15 mmHg	H
	<50 mmHg	Decrease of ≥ 15 mmHg	L
Weight	--	Increase of $\geq 7\%$	H
	--	Decrease of $\geq 7\%$	L
Respiratory Rate	>20 bpm	--	H
	< 10 bpm	--	L

BP = blood pressure, H = high, L = low.

- a. Clinically notable means that a value must meet the criterion value and must attain the specified magnitude of change relative to baseline.

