5.3.6 Other Considerations

Due to the early termination of the study, only simple summary of descriptive statistics will be provided for efficacy endpoint.

Individual subject data in the database will be presented in data listings.

The following rules/definitions will be applied in the final outputs:

- Homeostatic Model Assessment of Insulin Resistance (HOMA-IR Fasting insulin (mIU/L) x Fasting glucose (mmol/L) / 22.5)
- Dyslipidemia: Please use the following link: (https://www.nhlbi.nih.gov/files/docs/peds_guidelines_sum.pdf) and consider subject “with Dyslipidemia” if TC \geq 170 or LDL-C \geq 110 or Non- HDL-C \geq 120 or TG \geq 90 or HDL-C \leq 40. Values given are in mg/dL. **To convert to SI units, divide the results for total cholesterol (TC), low-density lipoprotein cholesterol (LDL-C), high-density**

lipoprotein cholesterol (HDL-C), and non-HDL-C by 38.6; for triglycerides (TG), divide by 88.6.

- Prehypertension or Hypertension:

BP is classified as SBP and DBP percentiles for age/sex/height.

Prehypertension: If SBP or DBP $\geq 90^{\text{th}}$ percentile or $< 95^{\text{th}}$ percentile or BP $> 120/80$ mmHG to $< 95^{\text{th}}$ percentile

Hypertension: If SBP or DBP $\geq 95^{\text{th}}$ percentile or BP $\geq 95^{\text{th}}$ percentile

- Subjects who are type 2 diabetes (T2DM) at Baseline are defined as follows:

Positive diagnosis of diabetes (Preferred Term: *Type 2 diabetes mellitus*) based on Medical History Form or AE with the start date prior to the first dose of the study drug.

The formula for BMI is weight in kilograms divided by height in meters squared.

Continuous variables will be summarized using the following descriptive summary statistics: the number of subjects (n), mean, standard deviation (SD), minimum value (min), and maximum value (max). Minimum and maximum values will be reported with the same precision as the units of measure. The mean and median will be reported to 1 greater decimal place, and the SD will be reported to 2 additional decimal places.

Categorical variables will be summarized using counts and percentages. Percentages will be presented to 1 decimal place.

Baseline Value: The baseline value will be defined as the most recent non-missing measurement (scheduled or unscheduled) collected prior to the initial administration of study drug. Unscheduled visit measurements will be included for derivation of baseline.

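### Table 2 counts high BP only above 180 systolic or 105 diastolic, so no by-visit count by arm covers the range that Section 5.3.6 calls abnormal in these adolescents

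*SAP*

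**What the plan says.** SAP Section 5.6.4 summarises vital signs and their changes from baseline by visit and arm. It then adds a flag: "The clinically notable vital sign values will be summarized using frequency count at each visit by treatment group". The footnote to Table 2 sets the rule: "Clinically notable means that a value must meet the criterion value and must attain the specified magnitude of change relative to baseline".

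The high BP entries are:
- systolic: above 180 mmHg, with "Increase of ≥ 20 mmHg";
- diastolic: above 105 mmHg, with "Increase of ≥ 15 mmHg".

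These are two rows, so a subject can be flagged on either one.

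Section 5.3.6 sets a different scale for the same subjects: "BP is classified as SBP and DBP percentiles for age/sex/height". Prehypertension covers the band from the 90th to below the 95th percentile, and also "BP $> 120/80$ mmHG to $< 95^{\text{th}}$ percentile". Hypertension is the 95th percentile or above. Section 5.1.2 uses these categories for one secondary endpoint, at Week 52.

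Section 3.2 gives the age range as 12 to 17 years. Section 3 says that the study stopped early, with about 20% of subjects having completed Week 52, and that most planned efficacy tables will not be produced.

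**The concern.** A by-visit count of notable values is meant to show individual movements that a mean can hide. Here the high BP rows start far above the level at which the same SAP calls BP abnormal in this age group. A subject can rise well into that abnormal range at any visit and not be counted.

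This matters more after early termination. Section 7 cancels the modelled efficacy, supportive, sensitivity and subgroup analyses, so descriptive safety output is a large part of what is left. Laboratory values get shift tables against reference ranges (5.6.3). ECGs get shift tables and tiered QTc counts (5.6.5). For BP, Table 2 is the only categorical display by visit and arm.

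**Working it through.** The SAP states no figure to reproduce. The check applies the written rule to whole-number readings.

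**Inputs.** Thresholds and the both-conditions rule: Table 2 and its footnote, Section 5.6.4. Abnormal BP: Section 5.3.6.

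**Rule.**
- Systolic high = (value > 180) and (value − baseline ≥ 20). First value counted = max(181, baseline + 20).
- Diastolic high = (value > 105) and (value − baseline ≥ 15). First value counted = max(106, baseline + 15).

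**Results.**

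| Row | Baseline | First value counted | Rise needed |
|---|---|---|---|
| Systolic | 110 | 181 | 71 |
| Systolic | 115 | 181 | 66 |
| Systolic | 120 | 181 | 61 |
| Systolic | 165 | 185 | 20 |
| Diastolic | 70 | 106 | 36 |
| Diastolic | 80 | 106 | 26 |
| Diastolic | 95 | 110 | 15 |

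The change condition has an effect only for baselines above 181 − 20 = 161 systolic or 106 − 15 = 91 diastolic. Below those baselines the level alone decides, and the 20 and 15 mmHg entries do nothing.

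**Comparison with 5.3.6.** A reading above 120/80 is prehypertension if below the 95th percentile and hypertension otherwise, so it is abnormal either way. The values that are above 120/80 but can never be counted as high are systolic 121 to 180 (60 whole-number values) and diastolic 81 to 105 (25 values).

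**Example.** 115/70 to 178/104: the rises are 178 − 115 = 63 and 104 − 70 = 34, well above 20 and 15. But 178 is not above 180 and 104 is not above 105, so neither row counts it. Both components exceed 120/80, so 5.3.6 classes the level as abnormal whether the 120/80 limb means both components or either one. No percentile table is needed for this.

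**Pulse, a separate point.** The high pulse row reads "Increase of 15 bpm", and the low row reads "Decrease of ≥ 15 bpm". The BP and weight change entries also carry ≥. Read as at least 15, a pulse going from 110 to 126 (+16) is counted. Read as exactly 15, it is not, and no baseline below 121 − 15 = 106 bpm could ever be counted.

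**The case against.** The strongest reply is that the two scales do different jobs. Table 2 is a safety flag that combines level and change. Section 5.3.6 defines a category, by level alone, for a secondary endpoint. A stricter flag beside a looser classification is not an error. That stands: a reader might infer that the SAP contradicts itself, and it does not.

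A second reply is that BP is reported elsewhere. Section 5.6.4 gives values and changes by visit and arm, with minimum and maximum among the statistics. Section 5.3.6 promises individual listings, and adverse events are tabulated under 5.6.2. An extreme reading such as 178/104 could well appear as a maximum. This also stands, and it rules out saying that large rises go unreported. It does not supply a count: a maximum shows one subject per arm and visit, a listing has no denominator, and an adverse event depends on being reported as one.

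A reader might also infer that the table will be almost empty whatever the drug does. The SAP gives no BP distribution, so this cannot be shown, and the low rows (below 90 systolic, below 50 diastolic) may have entries.

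Lastly, a reader might take the pulse row to miss a rise such as 85 to 125 bpm. The footnote asks that the change be attained, which reads naturally as reaching at least 15, and the other rows agree. It is probably a typing slip, or a sign lost in conversion, and adds nothing to the BP point.

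**Conclusion.** The point holds as a poorly fitted criterion. As written, no planned by-visit count by arm detects a rise into the range that Section 5.3.6 itself calls abnormal. The gap is 121 to 180 mmHg systolic and 81 to 105 mmHg diastolic. The one output on the 5.3.6 scale is the Week 52 endpoint, at a visit that about 20% of subjects completed. It may not be produced at all, since Section 5.4.3 lists only BMI analyses.

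The size is moderate. No estimate, test or error rate changes. What is lost is a categorical view of BP during treatment, and a low count in the high rows should not be read as reassurance.

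The conclusion rests on three readings: whole-number measurements; the footnote applied as written to the BP rows; and the 90th and 95th percentile limits in 5.3.6 taken as a band, although the text joins them with an or that every value would satisfy. Which thresholds are clinically right is not judged here.

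**What to change.** Keep Table 2 and add one descriptive table to Section 5.6.4. By visit, at end of treatment, and by arm, give the n (%) of subjects whose systolic or diastolic BP was below the 90th percentile at baseline and is at or above it post-baseline. Do the same for the 95th. Use the percentile classification in 5.3.6, and take as denominator the subjects below the limit at baseline who have a reading at that visit. No hypothesis test is needed, in line with Section 5.6.

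The cost is one more table and the derivation of percentiles at each visit. The SAP defines the categories but does not say that they will be derived other than for Week 52, so this may be new programming.

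As a separate clerical correction, reconcile the change entry in the high pulse row with the other change rows, which use ≥.

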5.6.5 Electrocardiograms

For each ECG parameter (including PR interval, RR interval, QRS interval, QT interval, QTc interval (Bazett formula), QTc interval (Fridericia formula), the actual value and change from baseline will be summarized by visit and treatment group using descriptive statistics.

Shift tables will present changes from baseline in ECG interpretation (categorized as normal; abnormal, not clinically significant; and abnormal, clinically significant) to end of treatment.

Maximum post baseline QTc (Bazett) and QTc (Fridericia) will also be tabulated by treatment group as follows:

- Number (percentage) of subjects with
 - greater than 450 msec,
 - greater than 480 msec, and
 - greater than 500 msec during the treatment, and
- Number (percentage) of subjects with an increment of greater than 30 msec and greater than 60 msec from the baseline visit.

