5.6.2 Adverse Events

A treatment-emergent AE (TEAE) is defined as an AE that emerges during treatment (up to 28 days after the last dose of study drug), having been absent at pretreatment (Baseline) or

- Reemerges during treatment (up to 28 days after the last dose of study drug), having been present at pretreatment (Baseline) but stopped before treatment, or
- Worsens in severity during treatment relative to the pretreatment state, when the AE is continuous.

Only those AEs that were treatment emergent will be included in summary tables. All AEs, treatment emergent or otherwise, will be presented in subject data listings.

The TEAEs will be summarized by treatment group. The following summaries will be reported for TEAES:

- Incidence of TEAEs in descending order of frequency
- Incidence of TEAEs by SOC and PT
- Incidence of treatment-related TEAEs by SOC and PT
- Incidence of TEAEs by SOC, PT and maximum severity (mild, moderate, or severe)
- Incidence of treatment-related TEAEs by SOC, PT, and maximum severity (mild, moderate, or severe)

Incidence of TEAEs by SOC, PT, and relationship to study drug (Yes [related] or No [not related])

A subject will be counted only once within a SOC or PT, if the subject experienced more than 1 TEAE within a specified SOC and PT.

The following summaries will also be presented for the treatment-emergent SAEs.

- Incidence of TEAEs leading to death
- Incidence of treatment-emergent SAE by SOC and PT
- Incidence of treatment-related treatment-emergent SAE by SOC and PT

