5.6.3 Laboratory Values

Laboratory results will be summarized using standard international units, as appropriate. For all quantitative parameters, the actual value and the change from baseline to each post baseline visit and to the end of treatment (defined as the last on-treatment value) will be

summarized by visit and treatment group using descriptive statistics. Percentages will be based on the number of subjects with both no missing baseline and relevant post baseline results.

Laboratory test results will be assigned a low/normal/high (LNH) classification according to whether the value was below (L), within (N), or above (H) the laboratory parameter's reference range. Within-treatment comparisons for each laboratory parameter will be based on 3-by-3 tables (shift tables) that compare the baseline LNH classification to the LNH classification at the End of Treatment and the Follow-Up visits. Similar shift tables will also compare the baseline LNH classification to the LNH classification for the highest and lowest value during the treatment period.

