8.1.1 Visit Windowing

Table 1 will be applied to all measurements including those from unscheduled visits and early termination visits to attain the measurement for analysis for the given scheduled visit.

Table 1 Windowing Rules for Safety Endpoints

Visit	Target Visit Day (in study days)	Visit Window (in study days)
Week 0	Day 1	Day 1
Week 1	7	2-21
Week 5	35	22-45
Week 8	56	46-70
Week 12	84	71-112
Week 20	140	113-168
Week 28	196	169-224
Week 36	252	225-280
Week 44	308	281-336
Week 52	364	337-379
Week56/FU		>379 or analysis visit date > last dose date +14
EOT		For last non missing analysis visit date ≤≤ 379 or ≤≤ last dose date +14 days.

In case of multiple assessments within the same visit window, the assessment closest to the target visit day will be used in data analyses; in the event of two assessments being equally close to the scheduled visit day, the latest assessment in the sequence will be used.

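### ECG interpretation is tabulated only from baseline to end of treatment, so a clinically significant reading that resolves by the last ECG is not counted

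*SAP*

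**What the plan says.** Section 5.6.5 plans three ECG summaries.

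- **Numeric intervals** (PR, RR, QRS, QT and two QTc corrections): "the actual value and change from baseline will be summarized by visit and treatment group using descriptive statistics".
- **Interpretation**, in three categories: a shift table from baseline, normal or "abnormal, not clinically significant; and abnormal, clinically significant) to end of treatment".
- **QTc extremes**: "Maximum post baseline QTc (Bazett) and QTc (Fridericia) will also be tabulated by treatment group as follows", with thresholds of 450, 480 and 500 msec and increases of 30 and 60 msec.

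Neither Section 5.6.5 nor any other part of the SAP plans a by-visit or worst-value summary of the interpretation.

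For laboratory tests, Section 5.6.3 plans shifts to end of treatment and follow-up and then goes further: "Similar shift tables will also compare the baseline LNH classification to the LNH classification for the highest and lowest value during the treatment period".

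End of treatment is one record per subject, but it is described in two ways. Section 5.6.3 has "end of treatment (defined as the last on-treatment value". Table 1 in Section 8.1.1 begins its EOT rule "For last non missing analysis visit date" and then sets the limit as Day 379 or 14 days after the last dose.

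**The concern.** A shift table is usually read as showing who moved to a worse category on study drug. This one shows who was still in a worse category at the last ECG. The two differ whenever an abnormality resolves.

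The SAP uses worst-value summaries for laboratory tests and QTc, and Section 5.6.4 counts notable vital signs at each visit. ECG interpretation is the exception. It is also the only planned categorical ECG summary that could show rhythm, conduction or morphology changes, because PR and QRS have no threshold counts.

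At stake is the by-arm number of subjects with a new clinically significant ECG on treatment. Efficacy is now descriptive only (Sections 5.4 and 7), so the safety tables carry much of the report.

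**Working it through.** The plan gives no figure to reproduce here. The check has three steps.

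**1. Subject paths through the rule.** N = normal, NCS = abnormal but not clinically significant, CS = abnormal and clinically significant. The paths are invented; the end-of-treatment cell follows from Section 5.6.5.

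| Baseline | On-treatment ECGs in order | Cell, end-of-treatment rule | Cell, worst-value rule |
|---|---|---|---|
| N | N, CS, N | N to N | N to CS |
| NCS | CS, NCS, NCS | NCS to NCS | NCS to CS |
| N | NCS, CS, NCS | N to NCS | N to CS |
| N | N, N, CS | N to CS | N to CS |

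In rows 1 and 2 a clinically significant finding is shown as no change. In row 3 it is shown as a milder shift. In row 4 it is present at the last ECG and nothing is lost. When the last record is itself on treatment, the worst category cannot be milder than the last one, so the difference runs one way: towards fewer subjects counted as having become abnormal.

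**2. What the other outputs still show.**

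- Transient QTc prolongation: counted, through the maximum post-baseline tabulation.
- Transient PR, RR or QRS extremes: visible in the minimum and maximum of that visit's row (descriptive statistics in Sections 5 and 5.3.6), but with no count of subjects.
- Any single record: Section 5.3.6, "Individual subject data in the database will be presented in data listings". Listings give no by-arm count.
- A finding reported as an adverse event: Section 5.6.2, "Only those AEs that were treatment emergent will be included in summary tables". This depends on the finding having been reported.

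The remainder is non-QTc rhythm, conduction or morphology findings. These have no aggregate worst-case count.

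**3. Possible size, under assumption.** The ECG schedule is not in this document, so k, the number of on-treatment ECGs, is assumed. The words by visit and maximum post-baseline imply more than one post-baseline ECG but do not fix k.

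*Assumption A:* the abnormality is present at exactly one of k ECGs, equally likely at each. The chance that it is the last is 1/k, so the share missed is 1 − 1/k:

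- k=1: 1 − 1 = 0%
- k=2: 1 − 1/2 = 50%
- k=3: 1 − 1/3 = 67%
- k=4: 1 − 1/4 = 75%

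This is an upper case under equal placement: a finding present at j of the k ECGs is missed with probability 1 − j/k, which is largest at j=1. A finding that persists to the last ECG is never missed.

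*Assumption B:* each ECG is independently CS with probability q between 1% and 5%. The share of ever-CS subjects shown by the end-of-treatment table is q / (1 − (1 − q)^k):

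- k=1: 100%
- k=2: 0.01/0.0199 = 50% to 0.05/0.0975 = 51%
- k=3: 0.01/0.0297 = 34% to 0.05/0.1426 = 35%
- k=4: 0.01/0.0394 = 25% to 0.05/0.1855 = 27%

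Both assumptions describe short-lived findings. Neither says how common such findings are.

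**The case against.** Section 5.6.5 contradicts nothing. A baseline-to-end-of-treatment shift is accurate for what it claims to show, and safety is descriptive with no hypothesis tests (Section 5.6). The laboratory extremes apply to numeric values, and the same idea is already applied to QTc. Transient findings can be traced in the listings and, if reported, in the TEAE tables. This stands, and it narrows the gap to the non-QTc remainder. It does not supply a by-arm count for that remainder.

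Two stronger readings are tempting, and neither is supported.

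- *A reader might infer that the table is biased towards hiding harm from the drug.* The same rule applies to both arms. It under-counts subjects who were ever abnormal, but nothing in the document shows that the loss differs between arms. Early termination does not settle this. With about 20% of subjects having completed Week 52 (Section 3), last ECGs fall at different exposure times, but shorter series also mean smaller k and a smaller loss.
- *A reader might infer that half to three quarters of clinically significant ECGs go unseen.* Those percentages hold only for single-occurrence findings and an assumed k. With one on-treatment ECG the loss is zero apart from unscheduled ECGs.

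A worst-value table has its own weakness: a subject with more ECGs has more chances of an abnormal reading.

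**Conclusion.** The point holds as a limited gap in safety reporting. The only planned table of ECG interpretation cannot show a clinically significant abnormality that has returned to its baseline category by the last ECG, and it shows a partly resolved one as a milder shift. The consequence is an under-count of subjects ever abnormal on treatment, confined in practice to non-QTc findings not reported as adverse events.

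The under-count follows from the rule itself, provided the end-of-treatment record is an on-treatment one. Its size cannot be derived from this document; the 0%, 50% and 75% at k=1, 2 and 4 are hypothetical. No efficacy or sample-size figure is affected.

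The EOT rule in Section 8.1.1 bears on the same point. It can admit an ECG taken up to 14 days after the last dose, by which time a finding may have resolved, and this sits uneasily with the last on-treatment value of Section 5.6.3.

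**What to change.** In Section 5.6.5 add, by treatment group, a shift table from baseline to the worst on-treatment ECG interpretation, analogous to the highest and lowest laboratory shifts in Section 5.6.3. Keep the end-of-treatment shift beside it.

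Three details need stating:

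- **Unscheduled ECGs are included.** Section 5.6.3 does not say this for its own extremes, and Section 5.3.6 names only listings, visit windows, baseline and last on-treatment visit as uses of unscheduled data. The worst reading should be taken before Section 8.1.1 selects one record per window; otherwise an abnormal ECG further from the target day would be dropped.
- **The on-treatment period is the SAP's own.** The descriptions in Sections 5.6.3 and 8.1.1 must be reconciled first.
- **The number of on-treatment ECGs, or the exposure, is shown by arm with the table**, because the chance of a worst reading depends on it.

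The cost is a few sentences and one extra table from ECG data already collected. The new table will also pick up isolated or artefactual readings; the retained end-of-treatment shift puts these in context.

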8 HANDLING OF MISSING DATA, DROP-OUTS, AND OUTLIERS

For determining treatment emergent markedly abnormal lab values, a missing baseline lab value will be assumed to be of grade 0.

No special handling of missing data is planned for the analysis of any of the efficacy or safety variables.

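### QTc threshold counts in SAP 5.6.5 mix subjects already above the limit at baseline with new crossings; adding new-onset counts would separate them at almost no cost

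*SAP*

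**What the plan says.** SAP 5.6.5 (Electrocardiograms) plans four kinds of ECG summary.

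- **Threshold counts.** "Maximum post baseline QTc (Bazett) and QTc (Fridericia) will also be tabulated by treatment group". The rows are the number and percentage of subjects "greater than 450 msec", above 480 msec and above 500 msec during treatment. Baseline plays no part.
- **Increment counts.** A separate bullet gives the "Number (percentage) of subjects with an increment of greater than 30 msec and greater than 60 msec from the baseline visit". It is not crossed with the thresholds.
- **Shift table.** "Shift tables will present changes from baseline in ECG interpretation", in three categories (normal; abnormal, not clinically significant; abnormal, clinically significant), to end of treatment. QTc categories are not used.
- **Descriptive statistics.** Actual value and change from baseline for each ECG parameter, by visit and arm.

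Other safety sections do bring in baseline. In SAP 5.6.4 the footnote to the vital-sign table requires both the criterion value and the stated change from baseline. SAP 5.6.3 plans shift tables from the baseline laboratory class to the class of the highest and lowest value on treatment. SAP 8 refers to a treatment-emergent notion for laboratory grades: "For determining treatment emergent markedly abnormal lab values, a missing baseline lab value will be assumed to be of grade 0".

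**The concern.** A reader of a QTc threshold table by arm usually wants to know how many subjects went above the limit after starting treatment. The planned rows answer a different question: how many were above it at any time after baseline, including those who were above it beforehand. A subject whose QTc falls, but whose highest post-baseline value is still over the limit, is counted in the same way as one who rises through it.

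Safety is summarised without hypothesis tests (SAP 5.6), so these raw counts will be read at face value. If by chance one arm starts with more subjects above 450 msec, the excess reappears in the on-treatment row, and nothing in that table shows where it came from.

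**Working it through.** The SAP states no QTc count or rate, so there is no figure of its own to reproduce. The check has three parts.

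**1. The rule applied to single subjects.** New crossing means baseline ≤ threshold and maximum > threshold.

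| Baseline → maximum (msec) | Change | >450 row | >480 row | >30 row | New crossing |
|---|---|---|---|---|---|
| 456 → 452 | −4 | yes | no | no | no |
| 485 → 481 | −4 | yes | yes | no | no |
| 460 → 445 | −15 | no | no | no | no |
| 445 → 470 | +25 | yes | no | no | yes (450) |
| 420 → 452 | +32 | yes | no | yes | yes (450) |
| 400 → 440 | +40 | no | no | yes | no |

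The first and fourth subjects have the same entries in every planned row, yet one fell and the other newly crossed 450. The last two both enter the >30 row, yet only one crossed a limit. New crossings therefore cannot be recovered from the threshold and increment rows together.

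**2. Illustrative size, no drug effect.** All inputs are assumptions; the SAP gives none of them. Let T ~ N(μ, 18²) be a subject's underlying QTc, let baseline be B = T + e₀, and let the maximum be M = max(T + e₁, …, T + e_k), with each e ~ N(0, 12²). Take μ = 405, 415 or 425 msec and k = 2 or 4 post-baseline ECGs.

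- Share already above = P(B > 450 and M > 450) / P(M > 450)
- Share not risen = P(M > 450 and M ≤ B) / P(M > 450)

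| μ | Already above, k = 2 / 4 | Not risen, k = 2 / 4 |
|---|---|---|
| 405 | 27% / 22% | 11% / 8% |
| 415 | 35% / 30% | 15% / 10% |
| 425 | 43% / 38% | 18% / 12% |

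In the same runs about 68% to 76% of subjects who newly crossed 450 rose by 30 msec or less, so the increment rows would miss most of them.

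A wider input grid (mean 400 to 420, between-subject SD 15 to 20, within-subject SD 8 to 12, 1 to 9 post-baseline ECGs) gives 9% to 61% already above 450. As one example in counts, mean 410, SDs 20 and 12 and three ECGs give 11.2 subjects per 130 counted as written and 7.5 per 130 newly crossing, so 11.2 − 7.5 = 3.7 were already above. The 130 per arm is the planned size in SAP 4; the trial stopped early.

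At the higher limits, with the inputs of the table above, the expected number counted who were already above at baseline is 0.01 to 0.36 per 130 for >480 msec and at most about 0.01 for >500 msec.

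**3. Effect on the comparison of arms.** Add an assumed 10 msec to post-baseline QTc in the drug arm and compare the difference in the percentage above 450 msec, for all subjects and for those at or below 450 at baseline.

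| μ, k | All subjects (points) | Baseline ≤ 450 (points) |
|---|---|---|
| 405, 2 | 5.3 | 4.9 |
| 415, 2 | 10.3 | 9.6 |
| 425, 4 | 18.4 | 18.9 |

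The differences are nearly equal. Only the ratio of percentages is weakened (for example 2.21 against 2.62 at μ = 415, k = 2), and the SAP plans no ratio.

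**The case against.** The strongest reply is that nothing here is wrong. The rows report subjects above a limit after baseline, and the SAP does not call them new or treatment-emergent. A subject going from 456 to 452 msec did exceed 450 msec on treatment. **This stands**: the point is an omission from the table, not a false count.

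Second, baseline is already used in the same section, through the increments, the by-visit changes and the interpretation shift table, and SAP 5.3.6 promises listings of individual data. This stands in part. The listings should allow a hand count, but none of the summaries described gives the number who newly crossed.

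Third, a reader might infer that prior prolongation hides a drug effect. The SAP does not support that: under randomisation both arms carry the same background in expectation, and the third check shows the difference between arms barely moving. What remains is chance imbalance at baseline, which the change-from-baseline summaries would only partly reveal.

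Fourth, the size is set by assumption. Any QTc eligibility limit would be in the protocol, which is not at hand. With an assumed screening cut at 450 msec on a separate ECG, the share falls to about 16% to 30%; if the eligibility ECG were itself the baseline, it would be zero. **This stands.**

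Finally, the SAP 8 sentence on laboratory grades is a rule for missing baselines and not a principle for all safety data. The vital-sign footnote and the laboratory shift tables are the better comparison, and they show only that the SAP uses baseline elsewhere.

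**Conclusion.** The point holds as a modest improvement. The threshold counts in SAP 5.6.5 are correct as labelled but pool existing with new exceedances, and no other ECG summary described in the SAP separates them. It matters mainly for >450 msec, where illustratively 22% to 43% of those counted were already above the limit. That range rests on assumed means, SDs and numbers of ECGs and on no QTc restriction at entry; under other inputs it could be well outside this range. At >480 and >500 msec the expected numbers are negligible.

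Two stronger readings should not be drawn. The counting rule is not an error, because the SAP claims nothing for it beyond what it counts. Nor does the rule materially bias the comparison of arms. The consequence is limited to how the counts are interpreted and to their exposure to a chance baseline imbalance, in descriptive tables of a trial that ended early.

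**What to change.** Keep the existing rows in SAP 5.6.5. For each threshold (450, 480, 500 msec) and each correction (Bazett, Fridericia), add by arm the number and percentage of subjects whose baseline QTc is at or below the threshold and whose maximum on-treatment QTc is above it. The denominator is the subjects at or below that threshold at baseline who have at least one post-baseline ECG.

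A shift table of baseline QTc category by maximum QTc category (≤450, >450 to 480, >480 to 500, >500 msec), one for each correction, would give the same information and also show how many subjects started above each limit.

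The cost is one sentence in the SAP and one added column, or one small table. It needs no new data and removes no planned output.
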